### STATISTICAL ANALYSES

#### 5.1 GENERAL CONSIDERATION

The purpose of this study is to assess the safety, tolerability, and efficacy of long-term administration of open-label gantenerumab in participants with AD who completed GRADUATE I or GRADUATE II.

The period of the POSTGRADUATE study and the OLE period from the parent studies will henceforth be referred to as the OLE period. Data from the OLE period, i.e., from OLE baseline (see Section 5.1.1 below for definition) to the end of study, will be summarized. Consequently, for participants who completed the OLE part of the parent studies and gave informed consent for the POSTGRADUATE study, the data collected in the OLE period of the parent studies will be included in the CSR of POSTGRADUATE. This will ensure that data from baseline and uptitration are included in the analyses for all participants of POSTGRADUATE. Participants of the OLE period of the parent studies without informed consent to POSTGRADUATE cannot be included in the analyses for the CSR of POSTGRADUATE and will instead be included in the analyses within the parent studies' CSRs.

All analyses will be purely descriptive and no imputation of missing data will be performed. For continuous data, descriptive statistics of mean, standard deviation, median, 1st and 3rd quartile as well as minimum and maximum and number of available data will be provided. For categorical data, number and frequency will be provided for each category as well as the number of available data.

All analyses of safety endpoints will be based on the SE analysis set unless mentioned otherwise while all analyses of efficacy endpoints will be performed for the ITT analysis set. The immunogenicity analysis set will be used for immunogenicity analyses.

Results will be shown separately based on previous treatment in the GRADUATE parent studies GRADUATE I and GRADUATE II, and by participation / non-participation in the OLE part of the parent studies and overall. For analyses using the ITT analysis set, this will be the treatment as randomized in the parent studies; for analyses using the SE analysis set, this will be the treatment actually received in the parent studies.

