The results are shown separately by participation / non-participation in the OLE part of the parent studies to mitigate the introduction of bias into the overall results. The non-inclusion of participants who discontinued during the OLE part of the parent studies and do not have an informed consent to POSTGRADUATE introduces an immortal time bias in certain analyses for this group of participants for the OLE part of the parent studies. The separation is further required due to different ARIA management rules in the parent studies and this study.

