### 5.3.2 Main Analytical Approach for Primary Endpoint(s)

All these safety analyses will be performed in the SE analysis set, except for analyses of ARIA-E or ARIA-H, CNS symptoms temporally associated with ARIA events or other MRI safety findings that will be based on the M-SE analysis set.

Participants will be analyzed according to the previous treatment they actually received in the parent studies and by participation / non-participation in the OLE part of the parent studies.

Descriptive statistics will be used to analyze all safety data collected in the study in the SE analysis set, unless otherwise specified.

Safety analyses will provide summaries of exposure to study treatment, adverse events, changes in laboratory test results (including shift tables), MRI findings, changes in vital signs and ECGs, and changes in C-SSRS scores as described in pertinent sections below.

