### 5.3.4 Magnetic Resonance Imaging Safety Findings

ARIA-E and ARIA-H are identified risks associated with gantenerumab. Sites were asked to capture ARIA findings as AEs in the POSTGRADUATE eCRF if they met any of the following criteria:

- Symptomatic ARIA-E (onset or worsening of CNS symptom[s] attributable to ARIA-E MRI findings in the judgement of the investigator), and/or
- ARIA findings that result in a change in study treatment (e.g., dosage modification, treatment interruption, or treatment discontinuation), and/or
- · Findings that are otherwise clinically significant in the investigator's judgment

Not all ARIA MRI findings qualify as AE. ARIA analyses will be mainly based on ARIA MRI findings. ARIA AEs will also be reported. ARIA analyses will be restricted to ARIAs documented during this study or the OLE part of the parent studies.

Based on MRI data, the incidence, severity (based on the Bioclinica severity scale (see Appendix 2) and the Barkhof Grand Total Score [BGTS]) and timing of ARIA-E and the incidence and timing of ARIA-H will be summarized overall and also by APOE  $\epsilon$ 4 genotype (by number of alleles) and by dose level. For participants from the OLE part of the parent studies, only ARIA-E severity measured by the BGTS is available for events that occurred during the OLE part of the parent studies. The timing of ARIA-E and ARIA-H may be summarized by descriptive statistics. Recurrence of ARIA-E within this study or the OLE part of the parent studies will be summarized. ARIA-E with associated and attributable CNS symptoms (see Section 5.3.4.1) and serious associated and attributable CNS symptoms will be summarized overall and also by APOE  $\epsilon$ 4 genotype (by number of alleles). Temporal co-occurrence of ARIA-E and ARIA-H will be summarized overall and also by APOE  $\epsilon$ 4 genotype. Temporal co-occurrence is defined as an MRI scan showing new ARIA-H that occurs between ARIA-E onset and resolution (inclusive), irrespective of the brain region.

MRI findings other than ARIA will also be summarized.

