### 5.6 OTHER SAFETY ANALYSES

### 5.6.1 Extent of Exposure

Exposure to study drug information will be summarized descriptively as follows:

- Treatment duration (in weeks)
- Total number of administrations
- Total cumulative dose (mg)
- Number of participants with any dose administration, separately for each dose level

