#### 5.8 INTERIM ANALYSES

### 5.8.1 Planned Interim Analyses

A first interim analysis will be conducted at the time of the primary analysis for the parent pivotal studies GRADUATE I and GRADUATE II, to support a potential filing of gantenerumab in case of positive read-out of the pivotal studies. A second interim analysis may be conducted for an update on safety data in the filing dossier. The analyses will be strictly descriptive and will not impact the conduct of the study, i.e., early termination for futility or efficacy will not be considered. As this study is open-label and all analyses are descriptive, the interim analyses are considered of an administrative nature and will not have an impact on the final study results.

The following will be included in the interim analyses:

- Participant disposition (see Section 5.2)
- Demographics and baseline characteristics (see Section 5.7.2)
- Extent of exposure (see Section 5.6.1)
- Adverse Events (see Section 5.3.3)
- MRI safety findings (see Section 5.3.4, excluding analyses of time to onset or time to recurrence of ARIA, and analyses by dose level. Not all analyses will be run by APOE ε4 genotype.)
- Laboratory data (see Section 5.3.5)
- Vital signs (see Section 5.3.6)
- ECG data (see Section 5.3.7)
- C-SSRS data (see Section 5.3.8)

Immunogenicity analyses may also be performed at the interim analysis.

No interim analyses of efficacy data will be done.

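### ARIA incidence by dose level is planned as crude percentages, with no time at level, although one uptitration step lasts at least 12 weeks and 510 mg Q2W up to 172

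*SAP*

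**What the plan says.** SAP 5.3.4 summarizes incidence, severity and timing of ARIA-E, and incidence and timing of ARIA-H, overall and also by APOE ε4 "genotype (by number of alleles) and by dose level". Frequency and timing of ARIA are among the primary endpoints (SAP 5.3.1).

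The stated methods are these:

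- SAP 5.3.2 fixes the analysis set for ARIA and "other MRI safety findings that will be based on the M-SE analysis set". That set is a set of participants.
- SAP 5.1 gives the general summary: "For categorical data, number and frequency will be provided for each category as well as the number of available data".
- SAP 5.6.1 lists treatment duration and cumulative dose, but its only item by level is "Number of participants with any dose administration, separately for each dose level".
- On timing, SAP 5.3.4 adds: "The timing of ARIA-E and ARIA-H may be summarized by descriptive statistics".

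The SAP does not define dose level, does not say to which level an MRI finding belongs, and gives no time at level. Protocol Table 1 shows 120 mg Q4W, 255 mg Q4W and 510 mg Q4W as separate uptitration steps for prior-placebo participants. Participants previously on active drug are at 510 mg Q2W from the start.

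SAP 5.8.1 lists MRI safety findings for the planned interim analyses, "excluding analyses of time to onset or time to recurrence of ARIA, and analyses by dose level". The by-level table therefore belongs to the final analysis.

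**The concern.** A by-level table will be read as a comparison of levels. A percentage of participants is a fair basis for that only if time at risk is similar across rows, and here it differs about 14-fold by design. Protocol 1.3.2.1 says that ARIA events tend to come early in treatment, so the contrast between uptitration and target is what a reader will look for. A long target row can collect more participants with a finding simply because it is long, and a step with a higher rate per unit time can then look like the safer row.

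The display grouped over all participants makes this worse. There the 510 mg Q2W row also takes in prior-active participants, who have up to 208 weeks at that level and no steps.

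**Working it through.** **Inputs**

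- Steps for prior-placebo participants uptitrating in WN42171 (protocol Table 1): 120 mg Q4W from Day 1 to Week 10, 255 mg Q4W from Week 12 to 22, 510 mg Q4W from Week 24 to 34. Each is 12 weeks. Protocol 4.3.2 requires three Q4W doses per step as a rule, so 12 weeks is the planned minimum.
- Doses of 510 mg Q2W after uptitration: up to 86 (protocol 3.2). Last dose at Week 206, final visit at Week 208.
- Scheduled scans (protocol Appendix 1, Tables 1, 2 and 4): Weeks 12, 24, 36, 48, 76, 104, 130, 156, 182 and 208. Scans tied to a dose are to be done at least 7 days before it.

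**Reproducing the plan's own figure.** Q2W visits from Week 36 to Week 206: (206 − 36)/2 + 1 = 86, as stated. Adding the 18 uptitration visits gives dose number 104 at Week 206, as in Appendix 1 Table 4.

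**Time and scans per level**

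| Level | Weeks | Scheduled scans, by last dose before scan |
|---|---|---|
| 120 mg Q4W | 12 | 1 (Week 12) |
| 255 mg Q4W | 12 | 1 (Week 24) |
| 510 mg Q4W | 12 | 1 (Week 36) |
| 510 mg Q2W | 208 − 36 = 172 | 7 (Weeks 48 to 208) |

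The ratio is 172/12 = 14.3. Gaps between scans at target are 12, 28, 28, 26, 26, 26 and 26 weeks: the first equals a step and the other six are longer. If scans were instead classed by the dose of the nominal visit, the counts would be 0/1/1/8.

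**Break-even.** With hazard h over time t, the crude percentage is 1 − exp(−h·t). A step shows less than target whenever h(step)·t(step) < h(target)·t(target), that is, unless h(target)/h(step) is below t(step)/t(target).

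| Comparison | Target 172 weeks | Target 86 weeks (assumption) |
|---|---|---|
| One step | 12/172 = 7.0% | 12/86 = 14.0% |
| Three steps combined | 36/172 = 20.9% | 36/86 = 41.9% |

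**Equal risk at every level (assumption).** For a risk p per 12 weeks, the target row shows 1 − (1 − p)^(172/12). For p = 0.5%, 1%, 2% and 5% this is 6.9%, 13.4%, 25.1% and 52.1%, about 10 to 14 times the step row. A rate per participant-year would show no difference.

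**A tenfold difference (assumption: 30 per 100 participant-years in the steps, 3 at target; 52.1775 weeks per year).**

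- One step: 1 − exp(−0.30 × 12/52.1775) = 6.7%.
- Three steps: 1 − exp(−0.30 × 36/52.1775) = 18.7%.
- Target, 172 weeks: 1 − exp(−0.03 × 172/52.1775) = 9.4%.
- Target, 86 weeks: 4.8%.

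Each single step falls below the 172-week target row although its rate is ten times higher. The three steps combined do not, and at 86 weeks there is no reversal.

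**Scanning works the other way.** If ARIA-E lasts D weeks with uniform onset, scheduled scans catch min(D, 12)/12 of onsets in a step and the sum of min(D, gap)/172 at target. For assumed D of 8, 12 and 16 weeks: 67%, 100% and 100% in a step, against 56/172 = 33%, 84/172 = 49% and 108/172 = 63% at target. A rate per participant-year would then understate ARIA-E at target by a factor of about 0.49 to 0.63 relative to a step.

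**The case against.** The strongest reply is that the detail may sit elsewhere. SAP section 1 leaves output layouts and the details of datasets and programs to Data Analysis Plan Modules 2 and 3, which are not available here. A rule may exist there. But the denominator of a primary safety summary is methodology, which the same section says is the SAP's subject. What can be said firmly is that the SAP is silent.

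A reader might infer that step findings will be credited to the wrong level. The documents do not support that. The scan precedes the new level's first dose by at least 7 days, so any derivation by date places it on the previous level, and SAP 5.3.4.1 already works with scan dates. Only a nominal-visit derivation would go wrong, and none is specified. A written rule is still worth one sentence.

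A reader might also infer that the by-level table will show the wrong order. That depends on hazards that neither document gives, and the example above reverses only for single steps at full target time.

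Two further points stand. Results are split by previous treatment and parent-OLE participation, so prior-active time enters the 510 mg Q2W row only in the overall display. The scan counts are scheduled scans only; unscheduled, early-termination and 4-weekly follow-up scans add to them.

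Last, no hypothesis is tested and ongoing safety decisions rest with the monitoring committee. This lowers the stakes but does not make the percentages comparable.

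**Conclusion.** The point holds for the by-level ARIA summaries and should be corrected before the final analysis. As the SAP is written, the percentages by level depend on length of stay as well as risk. The 14.3-fold difference in time and the break-evens of 7.0% and 20.9% follow from the schedule alone, using minimum step length and maximum target time; shorter target time raises the break-evens. The hazards and ARIA-E durations are illustrations, not estimates.

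The one-scan-per-step count is confirmed only for uptitration within WN42171, because the parent-OLE scan schedule is not in these documents. SAP 5.1 keeps parent-OLE uptitration data on purpose ("This will ensure that data from baseline and uptitration are included in the analyses for all participants of POSTGRADUATE") and warns that leaving out those who discontinued without consenting to this study "introduces an immortal time bias in certain analyses for this group of participants". That warning applies to any by-level rate in those groups.

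The point does not extend to the general adverse event tables: n (%) over a common planned period, with total event counts, is an acceptable summary there.

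**What to change.** 1. In SAP 5.6.1, add participant-years by dose level.
2. In SAP 5.3.4, keep n (%) and add first ARIA-E and first ARIA-H per 100 participant-years by dose level. End person-time when the event in question is first detected, so that a stay at one level prolonged by ARIA does not enlarge the denominator.
3. Define dose level, with 510 mg Q4W and 510 mg Q2W as separate levels, as in protocol Table 1.
4. Assign each finding to the last level dosed before the scan that detected it.
5. Show the number of scans per level beside each rate.
6. Present the rates within the planned previous-treatment and parent-OLE groups, and repeat the immortal-time caveat of SAP 5.1 beside parent-OLE uptitration person-time.

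Cumulative-incidence curves for first ARIA-E and first ARIA-H would be a useful option but are not needed to correct the by-level table.

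The cost is SAP wording and a few extra columns from data already collected; no clinical rule changes. There are two limits. The rates assume a constant hazard within each level, and sparser scanning at target still lowers detection there. The scan counts disclose that second limit but do not remove it.

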# 5.3.4.1 CNS Symptoms Temporally Associated with and Attributable to ARIA-E MRI Findings

CNS symptoms temporally associated with and attributable to ARIA-E are defined as onset or worsening of CNS symptom(s) that is/are temporally associated with ARIA-E MRI findings and considered by the investigator to be attributable to ARIA-E. CNS symptoms experienced by the participant that are new or worsened since the last MRI without ARIA-E are collected in a CNS Symptoms Request Form. To identify CNS symptoms temporally associated with and attributable to ARIA-E MRI findings, the following definitions will be used:

NEW CNS symptoms: If there is any AE reported in the eCRF with 'Reported on this study's CNS Symptom Collection Form' = Yes that is [new since date of most recent MRI scan showing no ARIA-E findings] AND is [ongoing or ends between the date of most

recent site visit prior to date of MRI scan showing new ARIA-E (MRI) and date of MRI scan showing ARIA-E resolution (MRI)] AND has the question "Is this AE attributable to ARIA-E?" answered with Yes in the eCRF AE page, then ARIA-E should be classified as associated with attributable CNS symptoms

OR

WORSENED CNS symptoms: If there is any AE reported in the eCRF with 'Reported on this study's CNS Symptom Collection Form' = Yes that is [started before the date of most recent MRI scan showing no ARIA-E findings] AND is [ongoing or ends between the date of most recent site visit prior to date of MRI scan showing new ARIA-E (MRI) and date of MRI scan showing ARIA-E resolution from MRI data] AND [there is an increase in severity grading] AND has the question "Is this AE attributable to ARIA-E?" answered with Yes in the eCRF AE page, then ARIA-E should be classified as associated with attributable CNS symptoms.

The CNS symptoms temporally associated with and attributable to ARIA-E MRI findings will be listed and summarized overall and also by APOE ε4 genotype (by number of alleles). The same summary and listing will be produced for all CNS symptoms temporally associated with (but not necessarily attributable to) ARIA-E MRI findings.

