5.3.5.2 ARIA Findings

Not every ARIA finding qualifies as an adverse event. An ARIA finding must be reported as an adverse event if it meets any of the following criteria:

- Symptomatic ARIA-E (onset or worsening of CNS symptom[s] attributable to ARIA-E MRI findings in the judgement of the investigator)
- ARIA findings that result in a change in study treatment (e.g., dosage modification, treatment interruption, or treatment discontinuation)
- Findings that are otherwise clinically significant in the investigator's judgment

Any accompanying symptom(s) should also be captured as separate adverse events. It is the investigator's responsibility to review all ARIA findings. Observations of the same clinically significant ARIA finding should only be recorded once on the Adverse Event eCRF (see Section 5.3.5.5 for details on recording persistent adverse events).

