Appendix 2: Management Rules for Amyloid-Related Imaging Abnormalities

Event	Characteristic	Action to Be Taken
ARIA-H	Without disseminated LH	 Continue study drug according to the schedule of administration (including uptitration). Perform MRI scans according to the standard MRI schedule.
	Disseminated LH	Permanently discontinue study drug.

 $\label{eq:ARIA-E} a myloid-related imaging abnormality-edema/effusion; ARIA-H=amyloid-related imaging abnormality-microhemorrhage/hemosiderin deposition; LH=leptomeningeal hemosiderosis; MRI=magnetic resonance imaging; PK=pharmacokinetic; Q4W=every 4 weeks.$

Notes:

- Disseminated LH is defined as more than three focal leptomeningeal hemosiderosis cumulatively.
- If ARIA-E and disseminated LH co-occur, the more conservative management rule will apply.
- The investigator may choose to perform additional MRI monitoring for ARIA at any time.
- In exceptional cases of 1) an ARIA-E that is asymptomatic with Bioclinica severity 1 and considered stable over consecutive MRI images by the Sponsor and investigator; or 2) symptomatic ARIA-E for which the imaging evidence of ARIA-E has resolved but the CNS symptoms continue, gantenerumab can be either reintroduced or uptitrated, as applicable, and Q4W MRI monitoring may no longer be necessary, as determined by the Sponsor and investigator.
- A PK sample will be obtained as soon as soon as practicable (e.g., at an unscheduled visit or the next study visit) following a MRI scan showing new occurrence or worsening of ARIA-E or ARIA-H that meets the discontinuation criteria (e.g., during an unscheduled visit).
- An additional plasma and RNA sample for the assessment of exploratory biomarkers will be obtained as soon as practicable (e.g., at an unscheduled visit or the next study visit) following each MRI scan showing ARIA-E until and including ARIA-E resolution (i.e., new, worsened, stable, improved, resolved ARIA-E).
- ^a Symptomatic ARIA-E is defined as onset or worsening of CNS symptom(s) that is/are attributable to ARIA-E MRI findings in the judgement of the Principal Investigator or appropriately medically qualified subinvestigator.

Signature Page for: System identifier:RIM-CLIN-439857 Protocol - WN42171 - GANTENERUMAB (MAIN) - v4 - Global/Core - Published

Company Signatory
11-May-2022 21:47:01 GMT+0000

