### 1.2.4 ARIA Management

In POSTGRADUATE, taking into account the evolving experience with managing ARIA findings, including the finding that continued gantenerumab treatment during episodes of asymptomatic mild ARIA-E was not associated with clinically unfavorable outcomes, the Sponsor intends to examine the safety of continuing gantenerumab treatment through mild to moderate asymptomatic ARIA-E findings and to examine the safety of gantenerumab therapy in the presence of an increased number of ARIA-H (microhemorrhages). In the parent studies, treatment was interrupted for participants

with asymptomatic ARIA-E with a BGTS ≥4 or symptomatic ARIA-E and discontinued for participants with more than 15 ARIA-H or with disseminated leptomeningeal hemosiderosis. In this study, ARIA management rules are based on the Bioclinica 5-point severity score (renamed as Severity Scale of ARIA-E (SSAE) since the writing of the study protocol) and treatment is interrupted for asymptomatic ARIA-E with a Bioclinica score ≥4 or symptomatic ARIA-E of any severity with CNS symptoms attributable to ARIA-E in the judgement of the investigator and discontinued for ARIA-H with disseminated leptomeningeal hemosiderosis. Disseminated leptomeningeal hemosiderosis is defined as more than three focal leptomeningeal hemosiderosis cumulatively.

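### SAP 5.3.4.1 adds an end-date window to investigator attribution, so ARIA-E that is symptomatic as the protocol defines it can be left out of the attributable-CNS-symptom count (minor)

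*SAP*

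**What the plan says.** Protocol Appendix 2, footnote a, states: "Symptomatic ARIA-E is defined as onset or worsening of CNS symptom(s) that is/are attributable to ARIA-E MRI findings", as judged by the principal investigator or a qualified subinvestigator. Protocol 5.3.5.2 uses the same test to decide when ARIA-E is recorded as an adverse event: symptoms "attributable to ARIA-E MRI findings in the judgement of the investigator". It adds: "Any accompanying symptom(s) should also be captured as separate adverse events". SAP 1.2.4 describes the dosing rule in the same terms, "symptomatic ARIA-E of any severity with CNS symptoms attributable to ARIA-E in the judgement of the investigator", and SAP 5.3.4 repeats the protocol's recording criterion.

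For reporting, SAP 5.3.4 plans a summary of "ARIA-E with associated and attributable CNS symptoms (see Section 5.3.4.1"), overall and by APOE ε4 genotype. SAP 5.3.4.1 supplies the algorithm. Symptoms "new or worsened since the last MRI without ARIA-E are collected in a CNS Symptoms Request Form". A new symptom then makes the episode count only if all of the following hold:

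- it is flagged as reported on the CNS form;
- it began after the last scan without ARIA-E;
- it is "ongoing or ends between the date of most recent site visit prior to date of MRI scan showing new ARIA-E (MRI") and the date of the scan showing resolution;
- the attribution question on the adverse event page is answered yes.

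The rule for worsened symptoms carries the same window. It also requires a start before the last clean scan and a rise in severity grade. A companion output drops attribution: "The same summary and listing will be produced for all CNS symptoms temporally associated with (but not necessarily attributable to) ARIA-E MRI findings".

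**The concern.** Two definitions are in use. The one that governs recording and study-drug handling rests on the investigator's attribution. The one that governs this table adds a date limit whose opening point is the last site visit before the scan. That limit is much narrower than the period over which the form gathers symptoms. A symptom can be collected and attributed, and the episode handled as symptomatic under the protocol, and the episode still not be counted.

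The count belongs to the primary safety analysis, and SAP 5.8.1 includes MRI safety findings in the planned interim analyses. SAP 1.2.4 says the study intends to examine continued dosing through mild to moderate asymptomatic ARIA-E, so readers will want the split between symptomatic and asymptomatic episodes to follow the protocol's definition.

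**Working it through.** No sample size, power or rate is involved, and the plan states no figure to reproduce. The check applies the rule to cases.

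**Direction.** Let A be the episodes with at least one symptom on the form that the investigator attributes to ARIA-E. Let B be the episodes with at least one such symptom that also meets the window. The conditions are joined by AND, so B is a subset of A and the window can only lower the count.

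**Cases.** All are new symptoms, on the form and attributed, so all are symptomatic under the protocol definition. V is the last site visit before the scan showing ARIA-E, M is that scan, and R is the resolution scan.

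| Symptom ends | SAP 5.3.4.1 |
|---|---|
| after the clean scan, before V | not counted |
| between V and M | counted |
| between M and R | counted |
| after R | depends on what *ongoing* means |
| not ended at data cut-off | counted |

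The first case fails on any reading. The fourth fails if *ongoing* means status at data cut-off, and passes if it means ongoing at some time within the window. Protocol Appendix 2 itself recognises symptoms that continue after the imaging finding has resolved.

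**Example from the schedule.** Protocol Appendix 1 places MRI at Weeks 104 and 130, at least 7 days before dosing. Assume each scan is exactly one week before its visit, visits fall on target dates, and the Week 103 scan is clean.

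- ARIA-E first seen: 130 − 1 = Week 129.
- Reach of the form: 129 − 103 = 26 weeks.
- Attributed symptom: Weeks 124 to 126, so it ended 129 − 126 = 3 weeks before the scan.
- Last site visit, if all doses are given on site: Week 128, so the window opens 129 − 128 = 1 week before the scan.
- Since 126 is earlier than 128, the symptom is not counted.

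**Dependence on place of dosing.** Appendix 1 allows mobile nursing at Weeks 106 to 128. If those visits were all at home and do not count as site visits, the last site visit is Week 104 and the window opens 129 − 104 = 25 weeks before the scan. Since 126 is later than 104, the same symptom is counted. SAP 5.3.4.1 does not say which reading applies.

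**Can another output recover the number?** The companion summary removes attribution but keeps temporal association, so the Week 124 to 126 symptom fails there too. ARIA adverse events are reported, but SAP 5.3.4 gives three alternative criteria for recording them (symptomatic, change in study treatment, otherwise clinically significant), so they do not isolate symptomatic episodes.

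**The case against.** The strongest reply is that the narrowing is open and within the SAP's authority. The section title and its opening sentence name a two-part category, temporal association and attribution. Requiring temporal proximity is a legitimate choice in an open-label study. Protocol 6.4 leaves endpoint definitions to the SAP, and SAP Section 1 says its language supersedes the protocol. This stands in part. A reader might infer that SAP Appendix 1 wrongly omits a change to a protocol-planned analysis, but the protocol planned no specific symptomatic count, so the documents do not support that. What remains is that SAP 1.2.4 and 5.3.4 themselves use the attribution definition, and nothing planned reports it.

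A second reply is that the example is unlikely. Adverse events are sought at every contact (Protocol 5.3.1), and Protocol 4.5.10 allows an unscheduled MRI for relevant CNS events. A symptom at Weeks 124 to 126 could well prompt a scan at the time. This is a good reason to expect few affected episodes. It does not make the rule agree with the definition.

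A third reply is that *site visit* is clear enough, because the protocol distinguishes site visits from home and mobile-nursing visits and marks Weeks 41 and 103 as site visits. That may be the intended reading, but under it the classification depends on where doses were given, so the SAP should say so.

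**Conclusion.** The point holds as a minor inconsistency between definition and algorithm. An attributed symptom that resolved before the last site visit is dropped, and if it was the only qualifying symptom its episode is missing from the count. The direction is certain. The size is unknown and probably small: ongoing symptoms pass, one qualifying event suffices, and unscheduled MRI is available.

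Three stronger readings are tempting and not supported.

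- **That most attributed symptoms are lost**, from setting a 1-week window against a 26-week form period. That compares stretches of calendar time, not symptoms or episodes. It also rests on assumed scan and visit dates: the baseline MRI may be up to 6 months old, and the Week 103 site visit may fall before or after the scan for Week 104. No percentage should be quoted.
- **That the events disappear.** Symptomatic ARIA-E and its symptoms are recorded as adverse events and stay in the adverse event outputs. Only the episode's classification is at issue.
- **That the SAP will label these episodes as without symptoms.** It defines no such category. They would simply be absent from the count, although a reader may draw that conclusion by subtraction.

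**What to change.** Keep the present summaries of temporally associated and attributable symptoms. Add one summary of ARIA-E episodes with any CNS symptom reported on that episode's CNS form and answered yes to attribution, regardless of end date, overall and by APOE ε4 genotype. Name it as the count of symptomatic ARIA-E. For participants with recurrent ARIA-E, state how a symptom is linked to its episode, since the layout of the form is not in the documents.

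For the retained window, state the reference date for *ongoing* and whether home-nursing visits count as site visits.

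The cost is one extra table and a few sentences, using the form flag and attribution field the algorithm already uses. The reported symptomatic ARIA-E rate may be slightly higher. Moving the window's opening back to the last clean scan would be less clean. It would widen the temporally associated summary and could admit more unrelated symptoms. It would also need a date of worsening, whereas Protocol 5.3.5.5 asks for initial and most extreme severity without mentioning when the severity changed.
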